Objective		Endpoint
		
 
ECGs.
 
LVEF as measured by echocardiogram.
 
NT-proBNP.
 
For participants testing positive for SARS-CoV-2 (by nucleic acid or serology test) during the intervention and follow-up periods, the number and proportion of participants with COVID-19 AEs/SAEs and the proportion asymptomatic.
 

		Number of participants seropositive for SARS-CoV-2 at end of study who were seronegative at randomization visit.

Table 5 Objectives and Endpoints

Objective	Endpoint
CCI	

**Objectives and Endpoints** Table 5

CCI
Exploratory Sub-study
CCI

AstraZeneca

```
AE = Adverse event; CCI
                                                                                         AESI = Adverse
event of special interest; AO = Airwave oscillometry; AX = Area of reactance; BCSS = Breathlessness, cough
and sputum scale; BD = Bronchodilator;
COPD = Chronic obstructive pulmonary disease; CompEx = Composite Exacerbations;
COVID-19 = Coronavirus disease 2019;
                                                              CT = Computed tomography;
                                                  ECG = Electrocardiogram; E-RS:COPD = Evaluating
Respiratory Symptoms of COPD; FEV1 = Forced expiratory volume 1 second; FVC = Forced vital capacity;
IL = Interleukin; LVEF = Left ventricular ejection fraction; CCI
NT-proBNP = N-terminal pro-brain natriuretic peptide; PD = Pharmacodynamics; CCI
                         PK = Pharmacokinetic; R5 = Resistance at 5Hz; R20 = Resistance at 20 Hz;
SAE = Serious adverse event; SARS-CoV-2 = severe acute respiratory syndrome coronavirus 2;
SGRQ = St. George's Respiratory Questionnaire; CCI
                                                                                           VAS = Visual
analogue scale.
```

AstraZeneca

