AO = Airwave Oscillometry; AX = Area of reactance; BCSS = Breathlessness, cough and sputum scale; COPD = Chronic obstructive pulmonary disease; COPDCompEx = COPD Composite Exacerbations; E-RS:COPD = Evaluating Respiratory Symptoms of COPD; PK = Pharmacokinetic; R5 = Resistance at 5 Hz; R20 = Resistance at 20 Hz; SGRQ = St. George's Respiratory Questionnaire; VAS = Visual analogue scale.

Objectives	Endpoints
CCI	
-	
-	
-	

Objectives	Endpoints
CCI	
CCI	

Table 4Safety objectives and associated endpoints

Objective	Endpoint
To assess the safety and tolerability of MEDI3506	During the intervention and follow-up periods:
compared with placebo in participants with COPD	• AEs, SAEs, AESIs.
and chronic bronchitis.	• Vital signs.
	• Clinical chemistry, haematology, and urinalysis.
	• ECGs.
	• LVEF as measured by echocardiogram.
	• NT-proBNP.
	
 
For participants testing positive for SARS-CoV-2 (by nucleic acid or serology test),
 

Objective	Endpoint
	during the intervention and follow-up periods, the number and proportion of patients with COVID-19 AEs/SAEs and the proportion asymptomatic.
	• Number of participants seropositive for SARS-CoV-2 at end of study who were seronegative at randomization visit.

AE = Adverse event; AESI = Adverse event of special interest; COPD = Chronic obstructive pulmonary disease; COVID-19 = Coronavirus disease 2019; ECG = Electrocardiogram; LVEF = Left ventricular ejection fraction; NT-proBNP = N-terminal pro-brain natriuretic peptide; SAE = Serious adverse event; SARS-CoV-2 = severe acute respiratory syndrome coronavirus 2.

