#### **COVID-19 related AEs and SAEs**

AE or SAE will be considered as related to COVID-19 if a participant has been tested positive for SARS-CoV-2 (by nucleic acid or serology test), during the intervention and follow-up periods and had an AE or SAE associated with COVID-19 based on the COVID-19 SMQ.

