# 4.1 General principles

Efficacy analyses will be performed using the ITT population. Demography and baseline characteristics will be summarised by study intervention group for the ITT population.

Study intervention groups will be displayed as follow:

- MEDI3506 CCI
- Placebo

A column reflecting all participants ("Total") will be included in tables that summarise study population data.

The below mentioned general principles will be followed throughout the study:

- Descriptive statistics will be used for all variables, as appropriate. Continuous variables will be summarised by the number of observations, mean, SD, median, upper and lower quartiles, minimum, and maximum. If n less than 3, the mean, SD, median, Q1 and Q3 will not be reported. For log-transformed data geometric mean, CV%, median, minimum and maximum will be presented. Categorical variables will be summarised by frequency counts and percentages for each category.
- Concentration data will be summarised using descriptive statistics, including n, n<lower limit of quantification, geometric mean, CV%, arithmetic mean, SD, minimum, median, and maximum values. The geometric mean is calculated as the exponential of the arithmetic mean calculated from data on a log scale.
- Unless otherwise stated, percentages will be calculated out of the population total for the corresponding study intervention group. Overall totals will be calculated for baseline summaries only.
- For continuous data, the mean and median will be rounded to 1 additional decimal place compared to the original data. The SD will be rounded to 2 additional decimal places compared to the original data. Minimum and maximum will be displayed with the same accuracy as the original data. CV%, where reported, will always be reported to 1 decimal place.
- PK concentration data will be presented in the listings to the same number of significant digits as the data received from the bioanalytical laboratory (usually to 3 significant figures) and against the same units as received. PK concentration descriptive statistics will all be presented to 1 additional significant figure than original data. Min, max will be presented as original data, n and n<LLOQ which will be presented as integers.
- In case the original value is reported for 3 or more decimals, then number of decimal places presented in the displays will be limited to 3 decimal places for every statistic.
- For categorical data, percentages will be rounded to 1 decimal place.

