TLF number	Title	Standard mock shell reference	Additional Information	Analysis1 (Week 12)	Analysis2 (Week 28)	Final Analysis
Table 14.3.2.5	Number of adverse events, by system organ class and preferred term (As-treated population)	AZ Corporate CSR/HLD Table Template S16(i)		X	X	X
Table 14.3.2.6	Number of subjects with adverse events, most common (frequency of >5%), by preferred term (As-treated population)	AZ Corporate CSR/HLD Table Template S8	Specify the period/periods which AE will be reported for, in the footnote Number (%) of subjects with AEs, sorted in decreasing frequency for preferred term (sorted by MEDI3506 treatment group) The cut off used is to be clearly stated in the title and footnote. The difference between S8 and FDAAA1 is – in S8 most common are defined as % in Total group, not individual treatment groups – and in FDAAA1 it is % in any treatment group.	X	X	X
Table 14.3.2.7	Non-serious adverse events occurring in greater than 5% of subjects (As-treated population)	AZ Corporate CSR/HLD Table Template FDAAA1		X	X	X
Table 14.3.2.8	Number of subjects with adverse events, by preferred term and maximum reported toxicity grade (As-treated population)	AZ Oncology CSR/HLD Table Template TAE050 - TA specific version of AZ Corporate CSR/HLD Table Template S10	Specify the period/periods which AE will be reported for, in the footnote Each subject has only been represented with the maximum reported toxicity grade for each preferred term. Subjects with events in more than 1 preferred term are counted once in each of those preferred terms. Each subject is counted only once (by their maximum reported toxicity grade) within a treatment group in this overall summary.	X	X	X

TLF number	Title	Standard mock shell reference	Additional Information	Analysis1 (Week 12)	Analysis2 (Week 28)	Final Analysis
Table 14.3.2.9	Number of subjects with adverse events, by preferred term and relationship as assessed by investigator (As- treated population)	AZ Corporate CSR/HLD Table Template S11	< <event rate="">> will not be included.</event>	X	X	X
Table 14.3.2.10	Number of subjects with adverse events, leading to dose interruption of IP, by system organ class and preferred term (As-treated population)	AZ Corporate CSR/HLD Table Template S_T1		X	X	X
Table 14.3.2.11	Number of subjects with COVID-19 related adverse events by system organ class and preferred term (As- treated population)	AZ Corporate CSR/HLD Table Template S9(i)		X	X	X

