Table 14.3.8.2.1	ECG variables, over time (As-treated population)	AZ Corporate CSR/HLD Table Template S25(ecg).	Use relevant timepoints for the study: SV1, SV3, SV8, SV12, SV14, E/D Labels as per SAP Analysis Visit Windows Report summary statistics (incl. Q1 and Q3)	X	X	X
Table 14.3.8.2.2	QTcF intervals, change from baseline to any postbaseline observation (As-treated population)	AZ Corporate CSR/HLD Table Template S35 (transposed)	Title and column headers should indicate which formula is being used and this should then be footnoted e.g., "QTcB calculated using Bazett's formula" or; "QTcF calculated using Fridericia's formula" or "QTc'X' calculated using <<>> formula". Define baseline measurement in the footnotes	X	X	X
Table 14.3.8.2.3	ECG values outside predefined criteria – key subject information (As- treated population)	AZ Corporate CSR/HLD Table Template AS4				X
Table 14.3.8.2.4	ECG, baseline versus maximum observation on treatment (As-treated population)	AZ Corporate CSR/HLD Table Template S41 (applied to ECG data).	Update column header from "Assessment at end of treatment" to "Maximum value during treatment"	X	X	X
Table 14.3.8.3.1	Left ventricular ejection fraction (%), over time (As- treated population)	AZ Corporate CSR/HLD Table Template S25(echoc)		X	X	x
Table 14.3.8.3.2	NT-proBNP data over time (As-treated population)	AZ Corporate CSR/HLD Table Template S25 (applied to Laboratory Data)		X	X	X

TLF number	Title	Standard mock shell reference	Additional Information	Analysis1 (Week 12)	Analysis2 (Week 28)	Final Analysis
Table 14.3.8.3.3	NT-proBNP baseline to maximum value during treatment (As-treated population)	AZ Corporate CSR/HLD Table Template S27		X	X	X
Table 14.3.8.3.5	Other safety tests – COVID- 19 related (As-treated population)	NEW1	Number of participants seropositive for SARS-CoV-2 at end of study who were seronegative at randomization visit.	X	X	X
Appendix 16.1.6	Subjects receiving the various batches of investigational products (All randomized subjects)	AZ Corporate CSR/HLD Listing Template APL22				X
Appendix 16.1.7	Randomization scheme and codes (All randomized subjects)	AZ Corporate CSR/HLD Listing Template APL23		-		X

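### The COVID-19 safety endpoint asks for two proportions among participants who test positive; the SAP tabulates the count but plans neither proportion nor their denominator

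*SAP*

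**What the plan says.** **Endpoint.** Protocol Section 3, Table 5 (Safety) sets the condition first: "For participants testing positive for SARS-CoV-2 (by nucleic acid or serology test) during the intervention and follow-up periods, the number and proportion of participants". What is counted is a COVID-19 AE or SAE, and the asymptomatic proportion follows. SAP Section 1.1, Table 4 repeats it: "during the intervention and follow-up periods, the number and proportion of patients with COVID-19 AEs/SAEs and the proportion asymptomatic". SAP Section 6, which lists departures from the protocol, does not drop or change it.

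**Definition of an event.** SAP 3.8.1: "AE or SAE will be considered as related to COVID-19 if a participant has been tested positive for SARS-CoV-2". Either type of test qualifies, at any time in intervention or follow-up, and the event must fall under the COVID-19 SMQ.

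**Default denominator.** SAP 4.1: "Unless otherwise stated, percentages will be calculated out of the population total for the corresponding study intervention group".

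**Planned outputs in Appendix A.**
- Table 14.3.2.11: "Number of subjects with COVID-19 related adverse events by system organ class and preferred term", As-treated population, template S9(i), no additional instructions.
- Table 14.3.4.1.3: the same for SAEs, As-treated population, template S17(i), no additional instructions.
- Table 14.3.6.8: COVID-19 AEs by maximum toxicity grade, As-treated population.
- Table 14.3.8.3.5 (shell NEW1): "Number of participants seropositive for SARS-CoV-2 at end of study who were seronegative at randomization visit". This is the separate, second COVID-19 endpoint.

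SAP 4.2.10.6 describes the seroconversion summary, adds the number vaccinated against COVID-19 during the study, and plans a listing of all SARS-CoV-2 results.

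**The concern.** The endpoint is conditional on a positive test, but the percentages that the plan will print are not. A percentage of the arm combines two things: how many participants were found positive, and how many of those had a reported illness. The endpoint as worded reports the second among those positive. Its asymptomatic component appears in the objectives table and then in no analysis section and no output, and the term is not defined.

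This matters because Protocol Section 2.3.1 names serious infection, including with SARS-CoV-2, as a potential risk of the drug. If the SAP is followed as written, the study report will show a figure that looks like the endpoint but has a different denominator, and one component will be missing. A post hoc table would then need choices (which test, which period, what counts as asymptomatic) made after the sponsor is unblinded at the Primary Analysis.

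**Working it through.** The plan states no figure for this endpoint, so there is nothing to reproduce. The check traces each component from definition to output.

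| Component | Planned output | Status |
|---|---|---|
| Number with COVID-19 AEs / SAEs | Tables 14.3.2.11 and 14.3.4.1.3, restricted to test-positives by SAP 3.8.1 | Produced |
| Proportion of test-positives with COVID-19 AEs / SAEs | None; the percentage defaults to the As-treated arm | Not produced |
| Proportion of test-positives asymptomatic | None; term undefined | Not produced |
| Number positive by either test, intervention plus follow-up | None | Not tabulated |

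**Why the arm is the denominator.** The two COVID-19 tables carry no instruction of their own, so SAP 4.1 applies. They also use the same templates as the general AE and SAE tables (14.3.2.4 with S9(i), 14.3.4.1.2 with S17(i)).

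**Whether another output supplies the missing denominator.**
- Table 14.3.8.3.5 is described as covering baseline seronegatives. On that description it omits participants seropositive at baseline, and nucleic-acid positives who did not seroconvert.
- The FEV1 subgroups in SAP 3.1.9 use each test separately, on the ITT population. A category is explored only if it holds at least 15% of participants: 0.15 × 144 = 21.6, so 22.
- Appendix 16.2.8.2 lists individual results, from which the number could be derived by hand. It is not a summary.

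**Size, on assumed counts.** The arm size of 72 is from SAP 1.3. All counts of positives and affected participants below are assumptions.

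Printed percentage = affected / 72. Endpoint proportion = affected / positives.

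1. Same printed figure, different endpoint. With 6 affected, the table prints 6/72 = 8.3% whatever the number positive. The endpoint is 6/6 = 100%, 6/9 = 66.7% or 6/18 = 33.3%.
2. Different printed figures, same endpoint. With 10 positives in one arm and 20 in the other, half affected in each, the table prints 5/72 = 6.9% against 10/72 = 13.9%. The endpoint is 5/10 = 50% against 10/20 = 50%.
3. Asymptomatic component. With 14 positives and 8 affected, the table prints 8/72 = 11.1%. The endpoint is 8/14 = 57.1%, and the remaining 6/14 = 42.9% would be asymptomatic if that means no COVID-19 related AE.

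**The case against.** The strongest reply is that most of what is needed is already there. Much of that stands, and it limits the point.

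- A reader might infer that the endpoint is never produced. It is produced in part: the number with COVID-19 AEs and SAEs is tabulated, and SAP 3.8.1 restricts it to test-positives as the endpoint requires.
- A reader might infer that no output shows any positives. Seroconverters are counted, subgroups by test result may be shown, and every result is listed. Only the total positive by either test is missing.
- Appendix A does not itself write the arm denominator beside the COVID-19 tables. It follows from the As-treated titles and the SAP 4.1 default. The templates and shell NEW1 are not in the documents, and the note for Table 14.3.8.3.5 is not exhaustive: it omits the vaccination count that SAP 4.2.10.6 promises. Even so, no text assigns either missing proportion to that table.
- A reader might go on to fault the positive-test condition because it stops the COVID-19 tables from being full incidences. The documents do not make this a defect. Table 14.3.2.4 counts all AEs by preferred term with no test requirement, and nothing shows that the SAP 3.8.1 rule governs Table 14.3.6.8. Removing the condition would take away the element that matches the endpoint.
- The conditional proportion has limits of its own. Infection is post-randomisation, so a comparison between arms among positives is not protected by randomisation. Serology may reflect infection before the study or, for all the documents say, vaccination, which Protocol 4.1.1.1 permits. Absence of a COVID-19 AE is also not quite absence of symptoms, since Protocol 8.3.8 generally keeps events unequivocally due to COPD out of AE reporting. These are reasons to label and define the rows, not to leave a stated endpoint without output.

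**Conclusion.** The point holds in a limited form. The count of participants with COVID-19 related AEs and SAEs is planned on the right participants. The two proportions that complete the endpoint have no planned output, nor does their denominator, and the percentage that will be printed is by default a proportion of the arm.

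The size cannot be stated from the documents because they give no number of positives; the examples above show only how far the two percentages can diverge. The conclusion rests on the SAP 4.1 default applying to tables with no other instruction, and on the unseen shells not adding what the text omits.

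This is one descriptive safety item. No hypothesis test, sample size or efficacy result depends on it. It should still be corrected, because the protocol and SAP both state the endpoint and following the SAP as written would not deliver it.

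**What to change.** Extend Table 14.3.8.3.5, by arm, with:

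1. n positive by nucleic acid, by serology, and by either test, during intervention and follow-up, with baseline-seropositive and COVID-19-vaccinated participants shown separately.
2. Of those positive by either test: n (%) with a COVID-19 related AE, n (%) with a COVID-19 related SAE, and n (%) asymptomatic.

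Define asymptomatic in SAP 3.8.1, for example as no COVID-19 related AE. State in SAP 4.2.10.6 that these percentages use test-positive participants as denominator, which meets the exception allowed by SAP 4.1. Label the rows descriptive because infection occurs after randomisation.

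Leave the positive-test condition in SAP 3.8.1 and the As-treated COVID-19 tables unchanged.

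The cost is a few rows in an existing table, one definition and one sentence on the denominator. Test results, AEs and vaccination records are already collected, so no new data are needed.

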# Appendix B ePRO scoring

### **B1** Calculation of E-RSTM: COPD scores

Table 27	E-RS TM : COPD	scoring
----------	---------------------------	---------

Domain	Item (number)	Patient's Response / Score
Breathlessness	Breathless today (7):	Not at all $= 0$
	Were you breathless today?	Slightly = $1$
		Moderately = 2
		Severely = 3
		Extremely = 4
	Breathless with activity (8):	Unaware of breathlessness = 0
	Describe how breathless	Breathless during strenuous activity = 1
	you were today:	Breathless during light activity = 2
		Breathless when washing or dressing $= 3$
		Present when resting = 3
	Short of breath – personal	Not at all = 0
	care (9):	Slightly $= 1$
	Were you short of breath	Moderately = 2
	today when performing your usual personal care activities like washing or dressing?	Severely = 3
		Extremely = 3
		Too breathless to do this $= 4$
	Short of breath – indoor	Not at all $= 0$
	activity (10):	Slightly = 1
	Were you short of breath today when performing your usual indoor activities like cleaning or household	Moderately = 2
		Severely = 3
		Extremely $= 3$
work?	work?	Too breathless to do this $= 3$
	Short of breath – outdoor	Not at all $= 0$
	activity (11):	Slightly = 1
	Were you short of breath	Moderately = 2
	today when performing your	Severely = 3
	home such as vard work or	Extremely $= 3$
	errands?	Too breathless to do this $= 3$
Cough and Sputum	Cough frequency (2):	Not at all $= 0$
	How often did you cough	Rarely = 1
	today?	Occasionally = 2
		Frequently = 3
		Almost constantly = 4

Domain	Item (number)	Patient's Response / Score
	Mucus quantity (3):	None at all = 0
	How much mucus (phlegm)	A little = 1
	did you bring up when	Some = 1
	coughing today?	A great deal $= 2$
		A very great deal = 3
	Difficulty with mucus (4):	Not at all = 0
	How difficult was it to bring	Slightly = 1
	up mucus (phlegm) today?	Moderately = 2
		Severely = 3
		Extremely = 4
Chest symptoms	Congestion (1):	Not at all = 0
	Did your chest feel	Slightly = $1$
	congested today?	Moderately = 2
		Severely = 3
		Extremely = 4
	Discomfort (5):	Not at all = 0
	Did you have chest	Slight = 1
	discomfort today?	Moderate = 2
		Severe = 3
		Extreme = 4
	Tightness (6):	Not at all = 0
	Did your chest feel tight	Slightly = 1
	today?	Moderately = 2
		Severely = 3
		Extremely = 4

CONFIDENTIAL AND PROPRIETARY

### **B 3** Calculation of SGRQ scores

Each questionnaire response has a unique empirically derived 'weight'. The lowest possible weight is zero and the highest is 100.

Each component of the questionnaire is scored separately in three steps:

- 1 The weights for all items with positive responses are summed.
- 2 The weights for missed items are deducted from the maximum possible weight for each component. The weights for all missed items are deducted from the maximum possible weight for the Total score.
- 3 The score is calculated by dividing the summed weights by the adjusted maximum possible weight for that component and expressing the result as a percentage:

Score =  $100 \times \frac{\text{Summed weights from positive items in that component}}{\text{Sum of weights for all items in that component}}$ 

The Total score is calculated in similar way:

Score = 
$$100 \times \frac{\text{Summed weights from positive items in the questionnaire}}{\text{Sum of weights for all items in the questionnaire}}$$

The Symptoms component is calculated from the summed weights for the positive responses to questions 1-8.

The Activity component is calculated from the summed weights for the positive responses to questions 11 and 15.

The Impacts component is calculated from the summed weights for the positive responses to questions 9-10, 12-14 and 16-17.

The questionnaire requests a single response to questions 1-17. If multiple responses are given to one of these questions then averaging the weights for the positive responses for that question will be done.

The Total score is calculated by summing all positive responses in the questionnaire and expressing the result as a percentage of the total weight for the questionnaire.

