#### PART 2

Response	Response weight	
9) How would you describe your respiratory condition?		
The most important problem I have	83.2	
Causes me quite a lot of problems	82.5	
Causes me a few problems	34.6	
Causes no problem	0.0	
10) If you have ever held a job:		
My respiratory problems made me stop working altogether	88.9	
My respiratory problems interfere with my job or	77.6	
made me change my job		
My respiratory problems do not affect my job	0.0	
Not applicable	0.0	
11) These are questions about what activities usually make you	a feel short of breath these days.	
Sitting or lying still = TRUE	90.6	
Washing or dressing yourself = TRUE	82.8	
Walking around the house = TRUE	80.2	
Walking outside on level ground = TRUE	81.4	
Walking up a flight of stairs = TRUE	76.1	
Walking up hills = TRUE	75.1	
Playing sports or other physical activities = TRUE	72.1	
12) These are more questions about your cough and shortness of breath these days.		
Coughing hurts = TRUE	81.1	

Response	Response weight		
Coughing makes me tired = TRUE	79.1		
I am short of breath when I talk = TRUE	84.5		
I am short of breath when I bend over = TRUE	76.8		
My coughing or breathing disturbs my sleep = TRUE	87.9		
I get exhausted easily = TRUE	84.0		
13) Questions about other effects your chest trouble may have of	on you.		
My cough or breathing is embarrassing in public = TRUE	74.1		
My respiratory problems are a nuisance to my family, friends or neighbors = TRUE	79.1		
I get afraid or panic when I cannot catch my breath = TRUE	87.7		
I feel that I am not in control of my respiratory problems = TRUE	90.1		
I do not expect my respiratory problems to get any better = TRUE	82.3		
I have become frail or an invalid because of my respiratory problems = TRUE	89.9		
Exercise is not safe for me = TRUE	75.7		
Everything seems too much of an effort = TRUE	84.5		
14) These are questions about your respiratory treatment.			
My treatment does not help me very much = TRUE	88.2		
I get embarrassed using my medication in public = TRUE	53.9		
I have unpleasant side effects from my medication = TRUE	81.1		
My treatment interferes with my life a lot = TRUE	70.3		
15) These are questions about how your activities might be affe	cted by your respiratory problems.		
I take a long time to get washed or dressed = TRUE	74.2		
I cannot take a bath or shower, or I take a long time to do it = TRUE	81.0		
I walk slower than other people my age, or I stop to rest = TRUE	71.7		

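### SAP Appendix B 3 contradicts itself on SGRQ scoring: one sentence averages multiple positive responses in every question, yet questions 11–16 are item lists that the same appendix sums

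*SAP*

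**What the plan says.** SAP Appendix B 3 (Calculation of SGRQ scores) sets out a three-step rule. The first step is a sum over items: "The weights for all items with positive responses are summed". After the weights of missed items are taken off the maximum, "The score is calculated by dividing the summed weights by the adjusted maximum possible weight for that component and expressing the result as a percentage". The components follow the same principle: "The Activity component is calculated from the summed weights for the positive responses to questions 11 and 15", and "The Impacts component is calculated from the summed weights for the positive responses to questions 9-10, 12-14 and 16-17". The Total is likewise described as a sum over all positive responses.

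Between the component definitions and the sentence on the Total, the appendix adds a rule on multiple answers: "The questionnaire requests a single response to questions 1-17". The next sentence is: "If multiple responses are given to one of these questions then averaging the weights for the positive responses for that question will be done".

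The item-weight tables that follow (Part 2) list questions 11–16 as sets of separate statements, each with its own weight. One example from question 11 is "Walking outside on level ground = TRUE", weight 81.4.

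SAP Section 3.4.4 and Protocol Section 8.1.8.5 describe a 50-item instrument with scores from 0 to 100, and both refer to the developer's manual for scoring details. The Week 12 change in SGRQ total score and the proportion improving by at least 4 points are secondary endpoints (SAP Table 2). SAP Section 4.2.5.5 also analyses the domain scores.

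**The concern.** The instrument ends at question 17, so a rule for questions 1–17 covers all of it. Only questions 1–10 and 17 offer one choice. In questions 11–16 a participant with COPD will often mark several statements as true, and the averaging sentence is the only text that speaks directly to several positive responses within one question. A programmer could reasonably take it as the specific instruction that overrides the general summing step. A second programmer could follow step 1. The two would produce different Activity, Impacts and Total scores from the same SAP.

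At stake are a named secondary endpoint, its responder version and two of the three domain scores. Protocol Section 8.1.8.5 ties a 4-unit change to the minimum clinically important difference, which presupposes the 0–100 scale.

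**Working it through.** **Inputs.** All weights are from the Item weights tables in SAP Appendix B 3. For one-choice questions the maximum is the heaviest response; for list questions it is the sum of the items.

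- Questions 1–8: 80.6 + 76.8 + 87.2 + 86.2 + 86.7 + 89.7 + 93.3 + 62.0 = 662.5 (Symptoms).
- Questions 9, 10 and 17: 83.2, 88.9 and 96.7.
- List questions:

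| Question | Items | Sum of weights | Mean weight |
|---|---|---|---|
| 11 | 7 | 558.3 | 79.76 |
| 12 | 6 | 493.4 | 82.23 |
| 13 | 8 | 663.4 | 82.93 |
| 14 | 4 | 293.5 | 73.38 |
| 15 | 9 | 650.8 | 72.31 |
| 16 | 5 | 398.7 | 79.74 |

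**Reproducing the plan's own figures.** The lists hold 7 + 6 + 8 + 4 + 9 + 5 = 39 items. With questions 9, 10 and 17, Part 2 has 42 items; with the 8 in Part 1, the instrument has 50, as stated. The maxima are:

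- Activity = 558.3 + 650.8 = 1209.1.
- Impacts = 83.2 + 88.9 + 493.4 + 663.4 + 293.5 + 398.7 + 96.7 = 2117.8.
- Total = 662.5 + 1209.1 + 2117.8 = 3989.4.

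With summing, a worst-possible record scores 100 on each component and on the Total, so the stated range is reproduced. The 39 list items carry 3058.1 of the 3989.4 total weight (77%).

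**The averaging sentence applied to questions 11–16.** Score = 100 × (one mean weight per list question + one-choice weights) / stated maximum. For the same worst-possible record:

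- Symptoms: 100 × 662.5 / 662.5 = 100.
- Activity: 100 × (79.76 + 72.31) / 1209.1 = 12.6.
- Impacts: 100 × (83.2 + 88.9 + 82.23 + 82.93 + 73.38 + 79.74 + 96.7) / 2117.8 = 100 × 587.1 / 2117.8 = 27.7.
- Total: 100 × (662.5 + 152.1 + 587.1) / 3989.4 = 35.1.

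The highest reachable scores, with only the heaviest item TRUE in each list, are Activity 14.2, Impacts 29.7 and Total 36.7.

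**Effect on change.**

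1. Take the last four items of question 11 as TRUE (sum 304.7, mean 76.18) and the last seven of question 15 (sum 495.6, mean 70.80). The participant then loses the 81.4 item from question 11 and the 71.7 item from question 15.
   - Summing: Activity falls from 66.2 to 53.5. The Total falls by 100 × (81.4 + 71.7) / 3989.4 = 3.84 points.
   - Averaging: the two means become 74.43 and 70.65. Activity falls from 12.16 to 12.00, and the Total falls by 0.05 points.
2. Take all seven items of question 11 as TRUE, with all seven then resolving. The Total falls by 100 × 558.3 / 3989.4 = 14.0 points with summing, and by 100 × 79.76 / 3989.4 = 2.0 points with averaging.
3. Averaging can also reverse direction. If only the lightest of the seven items (72.1) resolves, the question 11 contribution rises from 79.8 to (558.3 − 72.1) / 6 = 81.0, so an improvement scores as a worsening.

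**The case against.** The strongest reply is that the rest of the appendix rules averaging out. Summing is ordered in step 1, in both printed formulae, in the three component sentences and again for the Total. The averaging sentence can be read as an exception for a stray second answer where one was requested. If each TRUE statement is an item in its own right, several TRUE statements are single responses to several items and do not trigger the exception. The missing-item rule supports this: it tolerates four missed Activity items, although Activity contains only two numbered questions. The 0–100 range and the developer's manual would also alert a careful programmer.

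Most of that stands. It shows that summing is the intended rule and that averaging is not certain to be programmed. It does not remove the contradiction. The sentence refers to questions 1–17, and the component definitions in the same appendix use question numbers for the whole lists. SAP Section 3.4.4 presents the appendix as the principle of calculation under the manual, so the appendix is what a programmer would work from. The manual was not available for this review, so nothing can be said about its own wording.

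A reader might go further and infer that the reported SGRQ scores will collapse, or that the treatment comparison will lose a known share of its effect. The documents support neither. Two rules stand side by side, and any figure for lost effect or misclassified responders would need item-response frequencies that the documents do not give. Whichever rule is used applies to both arms alike.

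**Conclusion.** The sentence is wrong as written. Appendix B 3 gives two incompatible rules for 39 of the 50 SGRQ items, and one of them cannot produce the stated 0–100 range: a worst-possible record would score Activity 12.6, Impacts 27.7 and Total 35.1. On a Total that cannot exceed 36.7, the 4-point threshold no longer corresponds to the difference cited in the protocol. These figures rest only on the printed weights, the literal averaging sentence and the stated denominators with no missed items.

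The reach is limited. Symptoms is unaffected because questions 1–8 are one-choice. The primary FEV1 analysis is untouched, and so are the four Hochberg hypotheses in SAP Section 4.1.1 (COPDCompEx, daily cough frequency, R5-R20 and BCSS). It would therefore be wrong to infer that the trial's main conclusions are at risk. The reason to correct the text is that the scoring of a secondary endpoint should have only one reading.

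**What to change.** In SAP Appendix B 3, replace the two sentences on single responses and averaging with text to this effect:

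> Questions 1–10 and 17 request one response. If more than one is given to any of these, the weights of the positive responses to that question are averaged. In questions 11–16 each TRUE item is scored separately and its weight is added to the sum.

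Add a check to the scoring program that an all-worst record returns 100 for Symptoms, Activity, Impacts and Total.

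The cost is one corrected passage and one unit test, made before the scores are derived. No new data, visits or changes to the analysis models are needed.
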